5.5.5. Handling of Missing Segmental Scores for SES-CD, GHAS, and RHI

The analyses of change from baseline and the defined responder analyses for SES-CD, GHAS, and RHI, as applicable, will exclude the segments non-evaluable or missing at baseline, regardless of whether or not they become evaluable post-baseline. In addition, any missing segment scores (in the presence of at least 1 non-missing segmental SES-CD score) of SES-CD will be imputed by non-missing score used in the previous visit. This methodology is the primary analysis and will also be referred to as “complete cases” or “paired segments” as only segments scored at both baseline and the repeat endoscopy will be assessed. Exploratory analyses of the SES-CD scores based on available data without any adjustments or imputation will also be performed.

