4.2.3. Efficacy Endpoints for Extension Period

The efficacy endpoints for the induction period listed above in section 4.2.2 will be evaluated for all extension visits.

In addition, proportion of patients achieving remission and remaining corticosteroid-free in the prior 12 weeks will be evaluated at each time point of Week 36, Week 48, and Week 52, among the patients who received corticosteroids for CD at baseline. This analysis will be performed for CDAI Remission and SF&AP Remission.

Clinical Remission (Based on CDAI) at both Week 12 and Week 52 will also be summarized. Following efficacy graphs will be presented.

- CDAI change from Baseline (Observed) showing mean and 95% CI at each scheduled visit up to Week 52, overall and by Biologic Exposed vs. Biologic Naïve
- CDAI (Observed) showing mean and 95% CI at each scheduled visit up to Week 160, overall and by Biologic Exposed vs. Biologic Naïve
- Bar graph of CDAI Clinical Response (NRI) at Week 12 and Week 52, overall and by Biologic Exposed vs. Biologic Naïve
- Bar graph of CDAI Clinical Response (Observed) at Week 12 and Week 52, overall and by Biologic Exposed vs. Biologic Naïve
- Bar graph of CDAI Clinical Remission (NRI) at Week 12 and Week 52, overall and by Biologic Exposed vs. Biologic Naïve
- Bar graph of CDAI Clinical Remission (Observed) at Week 12 and Week 52, overall and by Biologic Exposed vs. Biologic Naïve
- Bar graph of Endoscopic Response-50 (Paired Segments, NRI) at Week 12 and Week 52, overall and by Biologic Exposed vs. Biologic Naïve
- Bar graph of Endoscopic Response-50 (Paired Segments, Observed) at Week 12 and Week 52, overall and by Biologic Exposed vs. Biologic Naïve
- Stool frequency change from Baseline (Observed) showing mean and 95% CI at each scheduled visit up to Week 52, overall and by Biologic Exposed vs. Biologic Naïve
- Stool frequency (Observed) showing mean and 95% CI at each scheduled visit up to Week 160, overall and by Biologic Exposed vs. Biologic Naïve

- Abdominal Pain change from Baseline (Observed) showing mean and 95% CI at each scheduled visit up to Week 52, overall and by Biologic Exposed vs. Biologic Naïve
- Abdominal Pain (Observed) showing mean and 95% CI at each scheduled visit up to Week 160, overall and by Biologic Exposed vs. Biologic Naïve

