9.2. Handling Endoscopy Data

9.2.1. SES-CD, GHAS, and RHI Related Endpoints

For the primary analysis of SES-CD score along with the sub-scores, only segments evaluated or imputed at both baseline and post-baseline will be summarized as described in section [5.5.5 Handling of Missing Segmental Scores for SES-CD, GHAS, and RHI](#). This will be referred to as either “Complete Case” or “Paired Segment” analysis. For example, if the rectum and left colon were evaluated at baseline and segments for the rectum, left colon, transverse colon and right colon were evaluated or imputed at Week 12, only the rectum and left colon at baseline and the rectum and left colon at Week 12 would be used to derive SES-CD and the change from baseline to Week 12 in this table.

SES-CD score will also be determined based on all available segments at a given visit without adjusting for the segments available at Baseline. These scores will be referred to as “Robarts Observed Scores”.

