9.3. Continuous Efficacy Endpoints

For continuous efficacy endpoints, the number of patients (n), mean, standard deviation (SD), standard error (SE), median, minimum and maximum will be presented for the actual values and change from baseline at all scheduled visits. It is noted that percent change from baseline may be displayed for certain endpoint variations, based on the TFL shell specifications. 95% CI presented in efficacy graphs will be computed using the t distribution.

All continuous efficacy endpoints will be tabulated by scheduled visit. This includes (see [Table 3](#)) Endoscopic Change, CDAI Change, GHAS Change, RHI Change, CRP Change, and FCP Change. Per Section 5.5.3, efficacy data will be associated with Visits according to analytic visit windows.

In all cases, the primary analysis will be based on observed cases.

The list of continuous efficacy endpoints is shown in [Table 5](#) below:

Table 5. Continuous Endpoints and Imputation Methods

Continuous Efficacy Endpoints	Method(s)
Endoscopic Change (Paired Segments, Total Score)	OC
CDAI Change	OC
SF Change	OC
AP Change	OC
GHAS Change from Baseline (Paired Segments, Total Score)	OC
RHI Change from Baseline (Paired Segments, Total Score)	OC
C-RP Change from Baseline	OC
FCP Change from Baseline	OC
Global RHI Score	OC

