APPENDIX 5. DOCUMENT REVISION HISTORY

Version	Date	Notes/Revisions
1.0	March 03 2016	Initial version.
1.1	November 23 2016	Updated with details and additional analyses.
1.2	January 26 2017	Updated with details on missing data and other details.
1.3	June 1, 2018	
Updated to reflect the Week 12 and Week 52 summary tables generated for topline analyses, definition of treatment failure, as well as to reflect endpoint alterations and additional details regarding CDAI, SES-CD, GHAS, and RHI algorithms. Analysis of compliance rate categories has been excluded.
 
Following endpoints have been removed from the SAP
 
 • PRO CD SF+AP response-25 • PRO CD SF+AP response-50 • PRO CD SF+AP response-30 + 2P • PRO2 CD response-25 • SF&AP clinical response-2 • SF&AP clinical response-1 • Endoscopic remission-2 • Histologic improvement • Histologic response 
Following endpoints have been added to the SAP
 
 • CRP-response-10 • FCP response-250 • Fistula Response • GHAS Improvement • GHAS Remission • RHI Improvement • RHI Response • RHI Remission • Global RHI Score • RHI Mucosal Healing
1.4	August 28, 2019	
LOCF removed.
 
Treatment Failure rule is used in NRI
 
Efficacy graphs added

1.5	January 06, 2020	
Changes from data review meeting
 
 • PFT abnormality has been revised • Missing segment imputation of SES-CD has been added

		
• Lower bound of 0 for Hematocrit sub-score of CDAI has been added• Treatment failure criteria has been revised• RHI response analysis on all patients has been removed• RHI remission by segment for subset of segment score > 3 is replaced by RHI remission by segment for non-RHI remitters• CRP Change among patients having CRP \geq 10 mg/L at Baseline has been added• Analysis window has been added to Safety follow-up visits• Unscheduled and early termination visits are included in all analysis windows• Patients requiring cardiac monitoring is determined programmatically• Listing of non-trial procedures added• Section on PK analysis is removed and combined with Section on PD• Description of SDTM data in Section 5 is removed
--	--	---

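### SAP 5.5.5 calls the primary SES-CD method 'paired segments' but carries missing segments forward; Week 12 responder categories and all Week 52 SES-CD results can differ from what the label implies

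*SAP*

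**What the plan says.** SAP 5.5.5 sets out the primary handling of SES-CD segments in three steps.

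- Segments without a baseline score are dropped: the analyses "will exclude the segments non-evaluable or missing at baseline, regardless of whether or not they become evaluable post-baseline".
- Where at least one segment is scored at a visit, any other missing SES-CD segment "will be imputed by non-missing score used in the previous visit".
- The method is then named 'complete cases' or 'paired segments', "as only segments scored at both baseline and the repeat endoscopy will be assessed".

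SAP 9.2.1 restates the method under the same two names, but there "only segments evaluated or imputed at both baseline and post-baseline will be summarized". SAP 9.2.2 gives GHAS and RHI the same pairing without the segment imputation.

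Other places describe the same results as unimputed. SAP 5.5.4 says continuous efficacy endpoints are not imputed. In SAP Table 5 the row "Endoscopic Change (Paired Segments, Total Score" carries the method OC, and 9.3 makes observed cases the primary basis. Protocol 13.2.1 rules out imputation of missing efficacy observations. SAP 4.2.3 lists a "Bar graph of Endoscopic Response-50 (Paired Segments, NRI) at Week 12 and Week 52" and a companion graph marked Observed under the same 'Paired Segments' label.

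The other SES-CD analysis in the readable text is exploratory: all segments available at a visit, not matched to baseline and not imputed (5.5.5; 'Robarts Observed Scores' in 9.2.1). Appendix 5 records at version 1.5, among changes from a data review meeting: "Missing segment imputation of SES-CD has been added".

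**The concern.** A carried-forward segment was not scored at the repeat endoscopy. It therefore cannot belong to an analysis limited to segments scored on both occasions. A reader of a 'Paired Segments' table or graph, especially one marked OC or Observed, would expect real scores at both visits. For GHAS and RHI that expectation is correct; for SES-CD it is not, and the label does not show the difference.

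Three things are at stake: the Week 12 endoscopic response and remission rates, all Week 52 SES-CD results, and whether any analysis shows what the re-examined segments did by themselves. The 'Robarts Observed' score does not fill that last role. A segment not reached at follow-up drops out of the follow-up total but stays in the baseline total, so it looks like improvement.

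**Working it through.** **The plan's own figures.** The only design figures are the 95% half-widths in SAP 5.1. With 1.96 × √(p(1−p)/n):

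- n = 30: 12.78% at p = 0.15 and 16.40% at p = 0.30
- n = 60: 9.03% at p = 0.15 and 11.60% at p = 0.30

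These match the stated 12.8%, 16.4%, 9.0% and 11.6%. They serve below only as a yardstick.

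**Inputs.** Response-50 is a fall of at least 50%. Remission is a score of at most 4, a fall of at least 2 and no sub-score above 1 (SAP Table 3). A sub-score is a segment score, 0 to 12 (SAP Table 2, Appendix 2). Scheduled endoscopies are at Screening, Week 12 and Week 52 (protocol Tables 2 and 3). The previous score is therefore baseline at Week 12 and normally Week 12 at Week 52.

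**Algebra.** For segments seen again, let O be the baseline sum and P the follow-up sum. For unseen segments, let m be the baseline sum and w the carried value.

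- True pairing: change = P − O; fractional fall = (O − P)/O.
- SAP rule: change = (P − O) + (w − m); fractional fall = [(O − P) + (m − w)]/(O + m).

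At Week 12, w = m. The change is P − O under both rules, so the primary endpoint is the same. The fall becomes (O − P)/(O + m), never larger than (O − P)/O when there is improvement. The total P + m is never smaller than P, and the sub-score limit covers more segments. Response and Remission can therefore be lost but not gained.

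At Week 52, w is the Week 12 score. The term m − w enters the change directly, so the result can move either way.

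**Worked cases.** The scores are illustrative; the ileum is unscored at the visit in each.

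| Case | Baseline (ileum + colon) | Carried ileum | Colon at visit | SAP rule | True pairing | All available segments |
|---|---|---|---|---|---|---|
| A, Week 12 | 6 + 9 | 6 | 3 | 15 to 9, −40%: no Response-50 | 9 to 3, −67%: Response-50 | 15 to 3, −80% |
| B, Week 12 | 6 + 6 | 6 | 1 | 12 to 7, −41.7%: neither | 6 to 1, −83.3%: Response-50 and Remission | 12 to 1, −91.7% |
| C, Week 52 | 8 + 6 | 1 | 4 | 14 to 5, −64.3%: Response-50 | 6 to 4, −33.3%: no Response-50 | 14 to 4, −71.4% |
| D, Week 52 | 6 + 6 | 5 | 1 | 12 to 6, −50.0%: Response-50, no Remission | 6 to 1, −83.3%: both | 12 to 1, −91.7% |

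Absolute change agrees at Week 12 (A: −6 and −6; B: −5 and −5). It differs at Week 52 (C: −9 and −2; D: −6 and −5).

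**Grid check.** All integer scores for one missing and one observed segment, with baseline total at least 6 and observed baseline at least 1:

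| SAP rule against true pairing | Week 12 | Week 52 |
|---|---|---|
| Configurations | 1,833 | 23,829 |
| Response-50 lost / gained | 364 / 0 | 4,145 / 1,206 |
| Remission lost / gained | 227 / 0 | 2,827 / 50 |
| Absolute change differs | 0 | 21,996 |

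These count possible configurations; they are not expected frequencies.

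**Size.** One reclassified patient is 1/60 = 1.7 points. Three would move 18/60 = 30.0% (Clopper-Pearson 18.8 to 43.2) to 15/60 = 25.0% (14.7 to 37.9). That is 5 points, against a planned half-width of 11.6 at a 30% rate.

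**The case against.** The case for leaving this as a wording point has real strength.

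- **The rule is disclosed.** SAP 9.2.1 states that imputed segments count and attaches the same labels. This stands: nothing is hidden. The fault is that 5.5.5, 5.5.4 and Table 5 say something else.
- **OC and Observed may describe patients, not segments.** In 4.2.3 Observed is the counterpart of NRI, which deals with patients who have no endpoint at the visit. Segment imputation works within a visit that has at least one scored segment. That reading is natural and probably intended. It leaves the 'Paired Segments' label with two meanings, one for SES-CD and another for GHAS and RHI.
- **True pairing is not the correct answer either.** In case A it declares a responder although 6 of the 15 baseline points were never re-examined. This stands, and is why the unimputed analysis belongs beside the primary one rather than in its place.

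A reader might go further and infer that no true paired-segment SES-CD analysis is planned anywhere. The documents do not support that. SAP 9.4 points to Table 6 for the proportion endpoints and methods, and Section 12 points to Section 9.5 for further analyses; neither is readable here. Section 12 also mentions, without detail, a sensitivity analysis of the endoscopic endpoints, and parts of it are redacted. One can say only that none is visible.

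A reader might also infer from the history (topline tables noted at version 1.3, LOCF removed at 1.4, segment carry-forward added at 1.5) that the rule was chosen because of the results. The log gives dates and a data review meeting, not a motive, and the Week 12 effect on responder rates is conservative.

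**Conclusion.** The contradiction is in the text and should be resolved. It does not threaten the primary endpoint: absolute SES-CD change at Week 12 is the same under both rules, assuming no unscheduled endoscopy supplied an earlier score to carry.

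At Week 12, percent change, Response-25, Response-50 and Remission can differ from true pairing, and category changes are losses only. At Week 52 the absolute change and the categories can move in either direction, because a segment gain seen at Week 12 is counted as still present without a second look.

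The overall size is unknown, since the documents give no rate of missing segments. The 1.7 points per patient assumes a denominator of 60, which fits the NRI analyses but need not fit the Observed ones. The point concerns SES-CD only; GHAS and RHI are paired without imputation. There is no hypothesis test to affect, so the consequence is for accurate description and for the precision of the reported rates.

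**What to change.** 1. Name the primary method 'baseline-evaluable segments, missing segments carried forward', and use that name consistently in SAP 5.5.4, 5.5.5, 9.2.1, Table 5 and the SES-CD figure titles in 4.2.3. Keep 'paired segments' for analyses without imputation.
2. Unless Table 6 or Section 9.5 already contains it, add a sensitivity analysis limited to segments actually scored at both baseline and the visit, for SES-CD change, Response-25, Response-50 and Remission at Weeks 12 and 52. The pairing rule without imputation is already specified for GHAS and RHI in 9.2.2.
3. Report the number of patients and segments imputed at each visit, so that the size can be judged.
4. List the rule in SAP Section 12 as a departure from protocol 13.2.1 introduced at version 1.5. Appendix 5 already records the addition; the readable part of Section 12 does not.

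The cost is text edits and a small amount of extra analysis and reporting. No new data are needed.

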6. PATIENT DISPOSITION

A summary of disposition of all screened patients will be generated and will include the following information:

- Number and percentage of enrolled patients in the Safety Population
- Number and percentage of enrolled patients in the ITT Population
- Number and percentage of enrolled patients dosed and not dosed
- Number and percentage of enrolled patients discontinuing during Induction, with reasons
- Number and percentage of enrolled patients discontinuing after Induction but prior to Extension, with reasons
- Number and percentage of enrolled patients who completed Week 12 and continued into Extension
- Number and percentage of enrolled patients discontinuing during Extension up to and including Week 52, with reasons
- Number and percentage of enrolled patients discontinuing during Extension after Week 52, with reasons
- Number and percentage of enrolled patients who completed Week 52
- Number and percentage of enrolled patients ongoing and completing the Protocol (Week 160)

Only the primary reason for discontinuation will be tabulated.

The reasons for Screen Failure will be separately tabulated according to the relevant Inclusion / Exclusion criteria. The number and percentage of ITT patients by Region, Country, and Site will be tabulated.

7. DEMOGRAPHICS, BASELINE CHARACTERISTICS, AND MEDICAL HISTORY

7.1. Demographics and Baseline Characteristics

The demographics and baseline characteristics will be presented using descriptive statistics for the ITT population.

Tabulated demographic characteristics will consist of

- Sex
- Age
- Age Category
- Ethnicity
- Race
- Weight (kg)
- Height (cm)
- Body Mass Index (BMI, kg/m²)

A patient's age in years is calculated using the integer part of the difference in number of days between the date of informed consent and date of birth divided by 365.25 or is recorded directly on the eCRF. The number and percentage of patients in the following age categories will be presented: 18-29, 30-39, 40-49, 50-59, 60-69, 70-75, < 65, ≥ 65, < median, and ≥ median.

Tabulated demographic characteristics will consist separately of region (North America, Europe), country (Canada, Hungary, Poland, USA, Ukraine) and history of tobacco/nicotine use (current, former, never).

7.2. Medical History

7.2.1. General Medical History

Medical history other than Crohn's disease (CD) will be summarized for the ITT population and will display the number and percentage of patients with a significant history for each body system.

7.2.2. Crohn's Disease History

The following CD history parameters will be summarized for the ITT population using descriptive statistics:

- Age at CD symptom onset (yr)
- Age at CD diagnosis (yr)
- Years since CD symptom onset
- Years since CD diagnosis
- Years since CD diagnosis category (0 - <2, 2 - <5, 5 - <10, 10 - <15, and ≥15)
- CDAI score at baseline
- CDAI score at baseline category (<330 and ≥330)

- Baseline Stool Frequency (daily average)
- Baseline Abdominal Pain (daily average)
- Category of days available for stool frequency and abdominal pain calculations (< 3, 3-6, >=7)
- SES-CD at baseline
- SES-CD at baseline category (< 12 and ≥ 12; ≥ median, < median)
- Baseline PRO2
- Baseline SF&AP
- Prior Corticosteroid use (Y/N)
- Prior Immunomodulator use (Y/N)
- Prior Biologics use (Y/N)
- Prior 5-ASA use (Y/N)
- Prior CD surgery History (Y/N)
- Baseline Fecal Calprotectin (microgram/g)
- Baseline Fecal Calprotectin (microgram/g) category (<250 and ≥250)
- Baseline CRP (mg/L)
- Baseline CRP (mg/L) category (<10 and ≥ 10)
- Baseline Enterocutaneous and/or Perianal Fistulas (Y/N)
- Draining Fistulas (Y/N)
- Non-Draining Fistulas (Y/N)
- Closed Fistulas (Y/N)
- Biological Response (Biologic Primary Non-responder vs All Others)
- Disease Location (Ileum only; Colon only; Ileocolonic (Ileum and Colon))
- Prior CD Surgery (Y/N)

Incomplete diagnosis dates will be imputed as detailed [Appendix 1](#).

7.2.3. Anti-TNF/Biologic Treatment History

The following Anti-TNF/Biologic treatment history parameters will be summarized for the ITT population using descriptive statistics:

- Number and percentage of patients with any Prior Anti-TNF or other Biologic Medications for the treatment of Crohn's Disease
- Previously Treated patients that took Medications Prior to Study Entry, with the number and percentage of patients having type of response (Primary Non-Responder, Secondary Non-Responder, Intolerant) and Length of time (<=1 year; >1 year and <=2 years; > 2 years) separately tabulated
 - Infliximab
 - Adalimumab
 - Certolizumab Pegol
 - Vedolizumab
 - Other

8.2. Investigational drug

All patients entering the Induction Period will initiate a 7-day dose titration regimen. This regimen will consist of RPC1063 0.25 mg starting on Study Day 1 for 4 days (1 capsule per day), then RPC1063 0.5 mg starting on Study Day 5 for 3 days (2 capsules per day), followed by RPC1063 1.0 mg beginning on Study Day 8 (1 capsule per day). Patients entering the Extension Period will continue with RPC1063 1.0 mg (1 capsule per day).

8.2.1. Extent of Exposure

Extent of exposure will be summarized for the Safety Population and will include the following:

- Duration of Exposure (Person-Years)
- Number of capsules administered

These outcomes are derived using data as collected in the EDC system. Duration of Exposure in person-years is calculated per-patient as $((\text{Date of Last Dose} - \text{Date of First Dose}) + 1)/365.25$. The number of capsules administered per-patient is directly obtained from the EDC system.

8.2.2. Investigational Drug Compliance

Drug Compliance will be summarized for the Safety Population and will include the following:

- Number of capsules expected
- RPC1063 Compliance Rate

These outcomes are derived using data as collected in the EDC system. Number of capsules expected is directly determined per-patient based on the number of capsules and bottles dispensed to the patient. The RPC1063 compliance rate is calculated per-patient as $(\text{number of capsules taken})/(\text{number of capsules expected}) \times 100$. The number of capsules taken is computed as the difference between the number of capsules dispensed at the previous visit and the number of capsules returned to the site at the following visit.

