9.7. Treatment Compliance

It is the Investigator’s responsibility to ensure that patients are correctly instructed on how to take their investigational drug and that each patient is fully compliant with their assigned dosage regimen. Records of investigational drug used and intervals between visits will be kept during the trial. Drug accountability will be noted by the Clinical Monitor during site visits and at the completion of the trial. Patients will be asked to return all unused medication at the end of the

trial. The investigational drug should be dispensed by the Investigator, or by a qualified individual under the Investigator's supervision. An up-to-date treatment inventory/dispensing record must be maintained as described in Section 10.3.

Overall trial non-compliance is defined as taking less than 80% or more than 120% of investigational drug during the entire treatment period.

At each visit, previously dispensed investigational drug capsules will be collected by the Investigator, or by a qualified individual under the Investigator's supervision, and compliance assessed. Patients exhibiting poor compliance as assessed by medication counts (i.e., 2 or more missed medication days in 1 week) and their response to a medication compliance question at each visit should be counseled on the importance of good compliance to the trial dosing regimen. Patients who are persistently non-compliant (<80% or >120%) should be discussed with the Medical Monitor to determine whether they should be withdrawn from the trial.

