10.2. Packaging and Labeling

RPC1063 capsules will be packaged in 30 cc white high-density polyethylene bottles (35 capsules per bottle, apart from the dose escalation kits), closed with a 28 mm child resistant screw-cap that is induction sealed. The labeling of investigational drug will be in accordance with GCP and any other local regulatory requirements.

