13.3. Disposition, Demographics and Baseline Characteristics

The number and percentage of patients in each population will be summarized. Patient disposition, including the number of patients enrolled, dosed, completing the Induction Period, and not completing the Induction Period by reason for dropout, entering the Extension Period, completing the Extension Period, and not completing the Extension Period by reason for dropout will be summarized. Patient demographics will be summarized and will include age, sex, race, ethnicity, height, weight, and body mass index.

Baseline characteristics will be summarized for and will include age at CD symptom onset, age at CD diagnosis, years since CD symptom onset, years since CD diagnosis, baseline CDAI score, baseline SES-CD score, baseline PRO2 score, prior anti-TNF use, and prior corticosteroid use.

Compliance with investigational drug will be summarized and will include the number of patients estimated to be < 80% compliant, 80 to 100% compliant, and > 100% compliant. The total dose and average daily dose will also be summarized.

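### The SAP compliance rate divides capsules used by capsules dispensed, so it cannot exceed 100% and counts an adherent patient's returned surplus as missed doses

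*SAP*

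**What the plan says.** SAP section 8.2.2 reports two quantities for the Safety Population: capsules expected and the RPC1063 compliance rate, which is capsules taken over capsules expected, times 100. For the denominator it says "Number of capsules expected is directly determined per-patient based on the number of capsules and bottles dispensed to the patient". The numerator, capsules taken, is defined in these words: "computed as the difference between the number of capsules dispensed at the previous visit and the number of capsules returned to the site". Returns are those counted one visit later. Neither part uses days on treatment or the prescribed daily count.

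Protocol section 10.2 gives the pack size as "35 capsules per bottle, apart from the dose escalation kits". Protocol section 9.7 says "At each visit, previously dispensed investigational drug capsules will be collected by the Investigator" or a qualified delegate, and sets the limits: "Overall trial non-compliance is defined as taking less than 80% or more than 120% of investigational drug during the entire treatment period". Protocol section 13.3 plans to count patients who are "< 80% compliant, 80 to 100% compliant, and > 100% compliant". SAP Appendix 5 records that the category analysis was removed at version 1.3, but the rate itself is still calculated and summarized.

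**The concern.** A compliance rate should compare what the patient took with what the regimen required. Here both parts of the ratio start from the dispensed count, which has three consequences.

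- Over-use cannot show as a value above 100%, although the protocol treats use above 120% as non-compliance and planned a category above 100%.
- Any capsule dispensed beyond need and handed back lowers the rate as though a dose had been missed.
- Surplus capsules that are taken, lost or not returned raise the rate towards 100%.

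Good adherence can therefore look like under-dosing, and over-use like good adherence. Longer-term safety of continued dosing is the Extension's primary objective, and one dose is enough to enter the Safety Population. Readers will want a valid adherence summary beside the safety results.

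**Working it through.** The documents state no compliance result, so there is no figure to reproduce. The check applies the SAP formula as written.

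**Inputs**
- Rate = 100 × (D − R)/D, with D dispensed and R returned (SAP 8.2.2).
- 35 capsules per bottle; escalation kit size not given (Protocol 10.2).
- Regimen (SAP 8.2): 1 capsule a day for 4 days, 2 a day for 3 days, "followed by RPC1063 1.0 mg beginning on Study Day 8 (1 capsule per day").
- Extension visits (Protocol Table 3): twelve 84-day intervals and one 28-day interval (Weeks 48 to 52).
- Assumption, not in the documents: the fewest whole bottles covering each nominal interval, that is 3 bottles (105) for 84 days and 1 bottle (35) for 28 days.

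**Ceiling.** Since R cannot be negative, (D − R)/D is at most 1. The maximum is 100%, whatever the supply.

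**Perfect adherence, Extension**
- Per interval: 84/105 = 80.0% and 28/35 = 80.0%.
- Prescribed over Weeks 12 to 160: 12 × 84 + 28 = 1036.
- Dispensed: 12 × 105 + 35 = 1295.
- Rate: 1036/1295 = 80.0%.
- With Week 12 (±3 days) and Week 160 (±7 days) at their limits: 1026/1295 = 79.2% to 1046/1295 = 80.8%.

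**True against reported adherence, same supply**

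| Taken, % of prescribed | Calculation | Rate as written |
|---|---|---|
| 80 | 0.8 × 1036/1295 | 64.0% |
| 100 | 1036/1295 | 80.0% |
| 120 | 1.2 × 1036/1295 | 96.0% |
| 125 (every capsule; 1295/1036) | 1295/1295 | 100.0% |

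**Single intervals, perfect adherence.** Where both visits carry ±7 days, a 12-week interval runs from 70 to 98 days: 70/105 = 66.7% to 98/105 = 93.3%. Three of the twelve (Weeks 12–24, 36–48 and 52–64) have a ±3-day visit at one end, so they run from 74 to 94 days: 74/105 = 70.5% to 94/105 = 89.5%.

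**Other Extension supply.** One extra bottle per visit gives 1036/(12 × 140 + 70) = 1036/1750 = 59.2%.

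**Induction, perfect adherence.** Prescribed: 4 × 1 + 3 × 2 + 77 = 87 capsules. The result depends on kit content and bottle number:
- 10-capsule kit plus one bottle per visit: 87/115 = 75.7%.
- Kit also holding the first 21 one-mg capsules, then one bottle at each of Weeks 4 and 8: 87/101 = 86.1%.
- 10-capsule kit plus two bottles per visit: 87/220 = 39.5%.
- With the Week 12 window of ±3 days (84 to 90 capsules), the extremes are 84/220 = 38.2% and 90/101 = 89.1%.

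**A case that needs no bottle assumption.** A fully adherent patient who stops on day 14 of an 84-day interval and was given exactly 84 capsules scores 14/84 = 16.7% for that interval.

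**With prescribed capsules as denominator.** Full adherence scores 100% at any visit spacing. Using 35 capsules in 28 days scores 35/28 = 125%, against 100% as written.

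**The case against.** The SAP says the denominator is based on supply dispensed, not that it equals it, so an unstated adjustment for days is possible. That stands as a matter of wording, but no adjustment is written and a programmer following the text would not apply one.

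The size of the effect rests on supply facts that are redacted or not given. This is fair: the percentages are illustrations, and the extra-bottle scenarios have no direct support in the documents. If surplus stayed with the patient until the end of the trial, 30 bottles (1050 capsules) would cover the Extension, and perfect adherence would score 1036/1050 = 98.7%. Protocol 9.7 does ask for unused medication back at the end, but it also has previously dispensed capsules collected at each visit, which does not fit carry-forward. Neither the ceiling nor the direction of the surplus effect depends on the bottle count.

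The protocol's limits are operational, applied by sites and the Medical Monitor, and the SAP dropped the categories. That narrows the harm, but the rate is still reported and those limits are the natural reference for a reader.

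Other outputs help. SAP 8.2.1 reports duration of exposure, and for capsules it says: "The number of capsules administered per-patient is directly obtained from the EDC system". Overdoses are reported separately under Protocol 12.2.10. However, the capsule count has no prescribed denominator, and the total and average daily dose promised in Protocol 13.3 are not in the SAP 8.2.1 list.

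Finally, unreturned capsules inflate any dispensed-minus-returned numerator, whichever denominator is used. This stands, and the fix needs a separate rule for it.

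**Conclusion.** The concern holds. As written, the rate is a supply-use ratio. The 100% ceiling is algebraic and needs only that returns are not negative. The downward bias follows whenever more is dispensed than is due before the next visit and the surplus is returned. Its size is illustrative: 80.0% for perfect adherence over the Extension under minimum whole-bottle supply with collection at each visit, and 38.2% to 89.1% across the Induction supply scenarios. A score of exactly 80% is not non-compliant under the protocol, but on the Extension supply shown it is the score for full adherence, where 100% would be expected.

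The consequence is confined to a misleading descriptive adherence summary that cannot be read against the protocol's 80% and 120% limits. No efficacy endpoint, analysis population or treatment-failure rule is affected, and the trial tests no hypothesis. The correction should be made because the summary is wrong as defined and easily put right.

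**What to change.** In SAP 8.2.2, define expected capsules as the number prescribed from first to last dose under the capsules-per-day regimen already in SAP 8.2, less documented directed interruptions. Compute compliance as (dispensed − returned)/prescribed × 100, so that values above 100% are possible and can be read against both protocol limits. State how unreturned bottles are handled, for example by flagging the interval instead of counting every capsule as taken.

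The cost is one or two SAP sentences and a small programming change. Dispensing, return and dose-date data are already used in SAP 8.2.1 and 8.2.2. The documents do not show whether interruption dates are captured in analysable form, so that should be confirmed. If they are not, the SAP should say that interruptions remain in the denominator.
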